## VI. Study Design

- Duration of Treatment

- A. The experiment for establishment of therapeutic environment.

Participants in the experiment for establishment of therapeutic environment underwent 1-3 evaluations. During this experiment, repetitive Transcranial Magnetic Stimulation (rTMS) was employed for brain modulation, involving two sets of stimuli. Each set consisted of initially administering continuous Theta Burst Stimulation (cTBS) to suppress the healthy side (approximately 600 pulses), followed by intermittent Theta Burst Stimulation (iTBS) to enhance the lesion side (600 pulses), totaling approximately 4 minutes (around 1200 pulses). The intensity of iTBS and cTBS is 80-120% of Motor Threshold.

Patients receiving rTMS treatment concurrently underwent machine-assisted bilateral upper limb training. During treatment sessions, patients were instructed to repeatedly perform grasping-opening tasks or engage in bilateral upper limb activities involving simultaneous shoulder and elbow movements while counting down loudly from 300. Upon completion of all training sessions, patients and therapists were required to complete usability and satisfaction analyses to evaluate equipment usability and operational satisfaction.

- B. The experiment for evaluation of therapeutic effects.

Patients will be divided into three groups: a Control group, an rTMS group, and an rTMS+BT group. Each group will receive a 65-minute treatment session, administered once every two days, totaling 10 sessions and completing the entire course within 20 days.

Control group: only received traditional rehabilitation training for 50 minutes and self-stretching training (15 minutes); rTMS group: received rTMS intervention (15 minutes) and 50 minutes of traditional rehabilitation training; rTMS+BT group: received rTMS intervention (15 minutes) along with BT meanwhile and 50 minutes of traditional rehabilitation training.

- Number of Planned Patients

72 participants are expected to be recruited in the trial.

- Investigational Product

1. Robot-assisted palm and finger rehabilitation device

Device name: "RM" Wearable Powered Hand Rehabilitation Device (Non-Sterile)

Manufacturer: Rehabotics Medical Technology Corporation

2. Bilateral proximal/distal upper limb training platform

- (1) The name of proximal upper limb training device: Non-powered upper limb proximal training platform

Manufacturer: Rehabotics Medical Technology Corporation

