- (2) The name of distal upper limb training device: Non-powered upper limb distal training equipment

Manufacturer: developed equipment by the Rehabilitation Department of Chang Gung Hospital

3. Repetitive transcranial magnetic stimulation (rTMS)

Device name: Repetitive transcranial magnetic stimulation (rTMS)

Manufacturer: Apollo Powermag 100, Mag & More, Germany.

- Endpoints

The primary endpoint was evaluated through the Fugl-Meyer Assessment, while secondary endpoints encompassed various measures, including the Modified Ashworth Scale (MAS), Manual Muscle Testing (MMT) for the upper extremity, Action Research Arm Test (ARAT), Brunnstrom Recovery Stage, Instrumental Activities of Daily Living Scale (IADLs). Additionally, participants and therapists responded to the System Usability Scale (SUS) questionnaire, and a Satisfaction questionnaire was administered.

- Criteria for Evaluation

1. Inclusion Criteria

- (1) Demographics and baseline characteristics of the participants were all available.

- (2) Participants completed all treatment sessions.

- (3) Functional assessments of the upper limb were performed at multiple time points: prior to, immediately after, and at 1 and 3 months follow-ups, without any omissions.

- (4) Both participants and therapists completed the System Usability Scale (SUS) questionnaire and the Satisfaction questionnaire.

2. Exclusion Criteria
  - (1) Participants with unforeseen psychological issues or significant changes in health conditions to prevent interference with the analysis.
  - (2) Participants using non-study-related medications that could potentially interfere with the outcomes.

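### The Criteria for Evaluation, most naturally read as the analysis population, confine the three-arm Fugl-Meyer comparison to completers

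*Protocol*

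**What the plan says.** Section VI of the protocol has a list headed Criteria for Evaluation, separate from the eligibility criteria in section II. Its inclusion part asks for complete baseline data and three further things:

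- sessions: "Participants completed all treatment sessions";
- functional assessments performed "prior to, immediately after, and at 1 and 3 months follow-ups, without any omissions";
- questionnaires: "Both participants and therapists completed the System Usability Scale (SUS) questionnaire and the Satisfaction questionnaire".

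Its exclusion part removes two groups:

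- "Participants with unforeseen psychological issues or significant changes in health conditions to prevent interference with the analysis";
- "Participants using non-study-related medications that could potentially interfere with the outcomes".

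Under Endpoints, "The primary endpoint was evaluated through the Fugl-Meyer Assessment". Statistical Methods compares the groups by t-test and by one-way ANOVA with post-hoc tests, and names no population for either. Experiment B has three arms and a course of ten sessions over 20 days. The protocol nowhere describes a set of all allocated participants.

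**The concern.** Attending all ten sessions, attending the 1- and 3-month visits and staying free of a significant health change cannot be known at entry. A set defined by them is selected after allocation. The primary comparison would then be between the remaining members of each arm, not between the arms as allocated.

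That comparison is biased when exclusion is related to outcome and differs between arms, either in its rate or in the strength of that relation. The arms receive different interventions, so equal exclusion cannot be presumed. Removing people whose health changes could also hide harm or poor response.

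Even without bias, the rule discards usable primary data. Read literally, one missed 1-month visit or one unreturned satisfaction form removes a participant who has a valid post-treatment Fugl-Meyer score.

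**Working it through.** **Is this an analysis population?** The words do not appear, so this is an inference. Three points support it.

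- The list cannot be an entry rule: eligibility is already in section II, and most of the conditions lie in the future at entry.
- The health-change exclusion gives its own purpose, which is to protect the analysis.
- Four assessments fit experiment B better than experiment A, for which the protocol says "Participants in the experiment for establishment of therapeutic environment underwent 1-3 evaluations".

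Two items are less clear. The medication exclusion carries no date, so it is the same problem only if it covers use after allocation. The questionnaire criterion names no arm or experiment. The questionnaires are described under experiment A as rating the equipment, which controls do not use, yet Endpoints lists them without limit: "Additionally, participants and therapists responded to the System Usability Scale (SUS) questionnaire, and a Satisfaction questionnaire was administered". This does not prove that controls are lost; it shows that the scope needs stating.

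**Inputs for an illustration.** The document gives only the total of 72, with no effect size, SD, power or dropout, so there is no figure of its own to reproduce. Everything else is assumed: all 72 in experiment B, 72/3 = 24 per arm, arms comparable as allocated, change SD 8 points, no true effect, and correlation ρ between outcome and propensity to be retained of 0.3, 0.5 or 0.7.

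**Bias.** If the lowest fraction p on that propensity is excluded, the mean of those retained shifts by ρ × 8 × φ(q)/(1−p), where q is the normal quantile of p. The ratio φ(q)/(1−p) is 0.195, 0.350 and 0.497 for p = 10%, 20% and 30%. For 10% versus 30% at ρ = 0.5, the bias is 0.5 × 8 × (0.497 − 0.195) = 1.21 points. Type I error is from simulation (pooled t-test at 0.05, 200,000 replicates per case).

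| Excluded, control vs active | Bias in points at ρ = 0.3 / 0.5 / 0.7 | Type I error |
|---|---|---|
| 10% vs 20% | 0.37 / 0.62 / 0.87 | 5.3 / 5.7 / 6.5% |
| 10% vs 30% | 0.72 / 1.21 / 1.69 | 5.8 / 7.6 / 10.6% |
| 30% vs 10% | −0.72 / −1.21 / −1.69 | 5.8 / 7.5 / 10.6% |
| 20% vs 20%, same ρ | 0 | about 5% |
| 20% vs 20%, ρ = 0 in control | 0.84 / 1.40 / 1.96 | 6.1 / 8.4 / 12.2% |

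**Retention.** Let s be the chance of attending a session and v the chance of attending a post-treatment assessment (three of them, baseline taken as done). If missed sessions are not made up and misses are independent, the retained share is s^10 × v^3. The clustered rows use a beta-binomial with intraclass correlation 0.2.

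| Retained of 72 at (s, v) | (0.97, 0.93) | (0.98, 0.95) | (0.99, 0.97) |
|---|---|---|---|
| Independent misses | 0.593 → 43 | 0.701 → 50 | 0.825 → 59 |
| Clustered within patient | 0.711 → 51 | 0.791 → 57 | 0.879 → 63 |
| Clustered, session and visit misses in the same patients | 0.837 → 60 | 0.882 → 63 | 0.928 → 67 |
| Sessions all made up, independent visits (v^3) | 0.804 → 58 | 0.857 → 62 | 0.913 → 66 |

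With all sessions made up and visit misses clustered, retention is 60, 63 and 67.

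**Precision.** The pairwise 95% half-width is t(0.975, 2n−2) × 8 × √(2/n). It is 4.65 points at n = 24, 4.75 at 23, 4.87 at 22, 5.26 at 19 and 6.22 at 14. Between 43 and 67 retained means about 14 to 22 per arm, so the interval is 5% to 34% wider than with everyone. With all sessions made up (58 to 67 retained, 19 to 22 per arm) it is 5% to 13% wider.

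Part of this loss occurs anyway, because a missed visit is also missing from an all-available analysis. That analysis has 22 to 23 per arm at one visit (0.93 × 24 to 0.97 × 24). Against it, the completer rule costs 2% to 28% without make-up (worst case 6.22/4.87) and 2% to 8% with it (worst case 5.26/4.87). Questionnaire, health and medication exclusions would come on top.

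**The case against.** The strongest reply is that the list is never tied to the Fugl-Meyer comparison. The document is a synopsis, and a SAP may define the sets. The evaluations mentioned for experiment A may mean visits rather than functional assessments. A criterion that is hard to apply to controls sits awkwardly in a population for three arms, so the list might be a data-completeness check covering both experiments. The link is indeed an inference. But no other reading fits better, and a SAP that analysed everyone allocated would contradict this list, so the protocol text would need changing anyway.

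Some points of wording stand. Only significant health changes are named, and they are undated. One of the four assessments precedes treatment, so not every condition arises after allocation.

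The protocol also says only that patients are divided between the groups and does not mention randomisation. If allocation was not random, analysing everyone allocated does not by itself make the arms comparable. It does avoid adding a second selection.

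Finally, the illustrated harm is modest in many cases. At 10% versus 20% excluded, the type I error reaches at most 6.5%. Error above 10% needs ρ = 0.7 together with either a 20-point gap in exclusion or a relation in one arm only. This limits any claim about size, but it does not justify the rule.

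**Conclusion.** The concern holds. On its most natural reading, the protocol states a completer population for its primary comparison and offers no alternative. This is a rule as written, not a detail left open for the SAP.

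Neither the size nor the direction of bias can be derived from the document. Under the assumptions above, the bias runs from zero (equal rates, same relation) to about 2 points, in either direction, with type I error from about 5% to 12%. The loss of precision against an all-available analysis is 2% to 28%, and 2% to 8% if every missed session is made up. Because the rule governs the primary endpoint and is cheap to change, it should be corrected. Confidence is medium, since the link to the Fugl-Meyer analysis is inferred.

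**What to change.** - Define the primary efficacy set as all participants allocated in experiment B, in their assigned arm, using every available Fugl-Meyer assessment. Sessions attended, questionnaires returned and later health changes should not affect membership.
- Keep the present completer set as a sensitivity analysis.
- Report the number and reasons of evaluation exclusions by arm.
- State whether the medication exclusion refers to use at entry or after allocation.
- Apply the questionnaire criterion only to a separate usability set of equipment users.

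The model can be left to the SAP, but a one-way ANOVA takes one value per person, so the text should say how the available assessments enter it.

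The change is to protocol wording, with no extra patients or planned visits. It has three costs. Participants who stop sessions are asked to attend the assessments already planned. The estimate may be somewhat diluted by incomplete treatment. Remaining missing data still need an assumption, which the completer sensitivity analysis does not remove.

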### ● Statistical Methods

Detailed demographic and medical history records are documented for each subject, including age, gender, time of stroke onset, location of stroke, and types of stroke. The clinical assessment will be conducted by a licensed occupational therapist with experience in treating neurological conditions. Clinical assessment results are being compared between groups using a student-t test. Pre and post-training within each group are being assessed using one-way ANOVA to determine improvement. One-way ANOVA is employed for inter-group comparisons, followed by post-hoc tests. If the data do not follow a normal distribution, non-parametric statistical methods are applied. Correlation analysis is used to explore relationships between clinical assessment results and various factors. Quantitative data are presented as (Mean±SEM), and a 95% confidence interval ( $p<0.05$ ) is considered statistically significant.

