## II. Indication

### 1. Inclusion Criteria

- (1) Age 40-80 years;
- (2) First-onset stroke patients;
- (3) Patients diagnosed with cerebral infarction or hemorrhage through CT or MRI;
- (4) Signed informed consent form by the patient and their family;
- (5) Stable physiological parameters;
- (6) Stroke occurred within the last 12 months;
- (7) Patients with unilateral hand function impairment caused by the stroke;
- (8) Upper limb muscle tone (Modified Ashworth Scale, MAS) less than 3 points;
- (9) Able to follow two-step commands.

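### The between-group Fugl-Meyer comparison leaves out time since stroke, which is recorded for every patient and may be anything up to 12 months

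*Protocol*

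**What the plan says.** Inclusion criterion 6 of the protocol reads "Stroke occurred within the last 12 months". It sets no lower limit, so entry may be days or almost a year after onset.

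Under Study Design, experiment B, "Patients will be divided into three groups: a Control group, an rTMS group, and an rTMS+BT group". No allocation method, ratio or balancing factor is given. The planned number is stated as "72 participants are expected to be recruited in the trial", without an effect size, SD, power or dropout rate. On endpoints, "The primary endpoint was evaluated through the Fugl-Meyer Assessment".

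Statistical Methods lists what is documented for each subject: "age, gender, time of stroke onset, location of stroke, and types of stroke". For the comparison of arms it names two methods: "Clinical assessment results are being compared between groups using a student-t test", and "One-way ANOVA is employed for inter-group comparisons, followed by post-hoc tests". Non-parametric methods replace these if the data are not normal. The only other place where onset time could enter is this sentence: "Correlation analysis is used to explore relationships between clinical assessment results and various factors".

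**The concern.** The primary endpoint is a motor-recovery scale, followed through a 20-day course and then to 3 months. It is reasonable to expect that patients entering soon after stroke are still recovering spontaneously, and that those entering near 12 months are doing so much less. Part of the spread in Fugl-Meyer results within each arm would then reflect when patients entered rather than what they received.

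A t test or one-way ANOVA on arm alone counts that spread as error. Such a test also leaves the estimated difference uncorrected if one arm happens to hold more early patients. An exploratory correlation with unnamed factors does neither job, because it does not alter the comparison of arms.

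The baseline Fugl-Meyer score, or a change from it, accounts for where a patient starts. It need not account for how fast that patient would recover anyway: two patients with the same entry score, one a few weeks and one 11 months after stroke, may have different expected gains. At stake is precision in a three-arm trial of at most 72 patients, and protection of the estimate if the arms differ in time since stroke.

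**Working it through.** **The plan's own figure.** The 72 cannot be reproduced, because no effect size, SD, power or dropout rate accompanies it. What follows is an illustration under stated assumptions.

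**Inputs**
- From the protocol: 72 patients, three groups, significance level 0.05, entry within 12 months of stroke.
- Assumed: all 72 are in experiment B and split equally, 72/3 = 24 per arm; a two-sided test; a pairwise difference of d = 0.8 SD.
- Assumed: time since stroke explains a share R² of the residual variance, from 0.04 to 0.26. The range comes from a simple exponential-recovery sketch with entry spread evenly over 0.5 to 12 months, not from the protocol.

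**Power.** Adjustment multiplies the residual variance by (1 − R²), so the standardised difference becomes d/√(1 − R²). The noncentrality is that value times √(n/2), with √(24/2) = 3.464. Power is from the noncentral t with the error pooled over three arms (72 − 3 = 69 df; the one further df for the covariate changes power by less than 0.001). The sample-size equivalent is 1/(1 − R²) − 1.

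| R² | d/√(1 − R²) | noncentrality | power | equivalent extra patients |
|---|---|---|---|---|
| 0 | 0.800 | 2.771 | 0.780 | 0% |
| 0.04 | 0.816 | 2.828 | 0.796 | 4% |
| 0.10 | 0.843 | 2.921 | 0.821 | 11% |
| 0.20 | 0.894 | 3.098 | 0.863 | 25% |
| 0.26 | 0.930 | 3.222 | 0.888 | 35% |

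With 18 per arm, the unadjusted figure is 0.653, rising to 0.699 at R² = 0.10 and 0.749 at R² = 0.20.

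**Check by another route.** By the normal approximation, 24 per arm gives 80% power for d = (1.96 + 0.84) × √(2/24) = 0.81. If the within-arm correlation of outcome with time since stroke is 0.2, 0.3 or 0.5, the residual SD is multiplied by √(1 − ρ²) = 0.98, 0.95 or 0.87, and power for that difference becomes 81.6%, 83.6% or 89.9%.

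**Differences between arms.** If time since stroke is uniform over 0 to 12 months, its SD is 12/√12 = 3.46 months. The standard error of a difference between two arm means is then 3.46 × √(2/24) = 1.00 month. Under random allocation, two given arms differ by at least 1 month in 32% of trials and by at least 2 months in 4.6%. For the largest of the three pairwise differences the figures are 58% and 11% (200,000 simulated trials). A 2-month difference moves the unadjusted contrast by ρ × 2/3.46 outcome SD: 0.17 at ρ = 0.3 and 0.29 at ρ = 0.5. Under random allocation these shifts are part of the sampling variation that the unadjusted standard error already describes.

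**The case against.** **Nothing stated is invalid.** Under random allocation an unadjusted t test or ANOVA keeps its type I error, and adjusting for a prognostic variable is a choice about efficiency. This stands. The point is an improvement, not the correction of an error.

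**Covariates belong in the SAP, which is not shown.** This would hold if the protocol had left the method open. It names tests that cannot carry a covariate, so the sentence naming them is the text to change. The objection does hold for allocation: the protocol is silent on balancing factors, and that silence cannot carry a finding.

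**Chance imbalance as a second harm.** A reader might infer that the unadjusted comparison is biased, on top of losing power, because the arms may differ in time since stroke. The documents do not support that. Under random allocation such differences are already in the unadjusted standard error, and counting them again would charge the same variation twice. Nor does the protocol's silence on randomisation show that a systematic difference exists. It means only that one cannot be excluded.

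**The size is assumed.** This stands too. The protocol gives neither a correlation nor an entry distribution, and if recruits fall in a narrow band of time since stroke the covariate explains little. The calculation also starts from a model without the baseline score. It measures the increment beyond baseline only if both R² and the 0.8 SD are taken relative to the variance left after baseline adjustment, and no figure in the documents allows that check.

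**Why this variable and not age, lesion site or stroke type?** They could also be considered. Time since stroke is singled out because the protocol admits a full year of it and the endpoint measures recovery.

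**Conclusion.** The point holds as a worthwhile improvement to the stated analysis. The protocol records time of onset for every patient, admits a 12-month range, and then fixes between-group tests with arm as the only term. Variation related to time since stroke stays in the error, and the estimate is not corrected for any difference between arms in that variable.

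Assuming 24 per arm, a 0.8 SD difference and 4% to 26% of residual variance explained, power rises from 0.78 to between 0.80 and 0.89. The lower end is under 2 percentage points, and a weak correlation makes the gain negligible. It would go too far to say that the trial is underpowered for this reason or that its estimate is biased: the documents contain no figure that shows either.

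**What to change.** In Statistical Methods, replace the t test and one-way ANOVA for the between-group Fugl-Meyer comparison with one linear model containing arm, baseline Fugl-Meyer score and time since stroke at entry (for example as log days). Take the pairwise arm contrasts from that model. Fix the form of the time variable before any outcome data are compared.

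The cost is a rewritten sentence and one degree of freedom for time since stroke. The variable is already collected, and no visit, assessment or treatment changes.

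Balancing allocation within bands of time since stroke is optional. It can be considered only once the protocol states how patients are allocated, and the model above does not depend on it.

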### **IV. Study Rationale:**

The study aims to establish a therapeutic model that combines Bimanual Therapy (BT) with repetitive transcranial magnetic stimulation (rTMS) to investigate neuroplasticity modulation in stroke patients with upper limb hemiparesis. In the study, inhibitory rTMS will be applied to the unaffected hemisphere, and facilitatory rTMS will be applied to the affected hemisphere during stimulation. Patients will also receive BT concurrently with these rTMS stimulations. Functional assessments of the upper limb will be performed prior to, immediately after, and at 1 and 3 months follow-ups to evaluate rehabilitation outcomes. This study will assess rehabilitation outcomes and explore the associated mechanisms of brain modulation, with the goal of improving clinical applicability.

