### **V. Study Objectives:**

This study comprises three main objectives. First, to establish a treatment process and environment for utilizing rTMS to modulate neural activity in patients with upper limb hemiparesis caused by stroke. Second, to investigate the application of inhibitory stimulation, continuous theta burst stimulation (cTBS), to the unaffected hemisphere of the stroke-damaged brain, followed by

facilitatory stimulation, intermittent theta burst stimulation (iTBS), to the affected hemisphere. The intention is to employ the established treatment process in the first part to formulate a clinical treatment model. Third, we will further study functional assessments of the upper limb before treatment, immediately post-treatment, and at 1- and 3-month follow-ups.

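### Two tests with no stated order for the three-group comparison, no time point for the primary Fugl-Meyer Assessment, and an unpaired test named for before-and-after data

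*Protocol*

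**What the plan says.** Experiment B in section VI of the protocol has three groups: Control, rTMS and rTMS+BT. For comparing them, the Statistical Methods text gives two rules. The first is "Clinical assessment results are being compared between groups using a student-t test". Two sentences later comes "One-way ANOVA is employed for inter-group comparisons, followed by post-hoc tests". Neither rule names an outcome, a pair of groups or a time point, and nothing ranks one above the other.

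Between the two stands the rule for change within a group: "Pre and post-training within each group are being assessed using one-way ANOVA to determine improvement". It carries no paired or repeated-measures qualifier.

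Under Endpoints, "The primary endpoint was evaluated through the Fugl-Meyer Assessment, while secondary endpoints encompassed various measures". No time point is attached to the primary measure. The Study Rationale has the assessments "performed prior to, immediately after, and at 1 and 3 months follow-ups to evaluate rehabilitation outcomes", the Study Objectives give the same schedule, and the Criteria for Evaluation require them "prior to, immediately after, and at 1 and 3 months follow-ups, without any omissions". That is one baseline and three post-treatment assessments.

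**The concern.** A t-test compares two groups. Applied to three, it implies a choice of pairs, and the protocol does not make that choice. ANOVA with post-hoc tests answers the same question by another route. Two analysts, each following one sentence of the protocol, could reach different verdicts on the primary outcome from the same data. Even with one agreed test, three FMA time points remain as candidates for the primary result.

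The within-group rule raises a different problem. An ordinary one-way ANOVA treats its measurements as independent, whereas before and after scores come from the same patient. At stake are the error rate of the primary claim, the freedom to choose test and time point after the data are seen, and power to detect change within a group.

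**Working it through.** **Inputs from the protocol:** three groups, 72 participants for the whole trial, and p<0.05.

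**Assumptions:** two-sided tests; equal groups, all in experiment B, so 72/3 = 24 per arm; normal data with equal variances. As a lower case, 20 per arm is also shown, because the evaluation criteria keep only participants for whom "Participants completed all treatment sessions" and every assessment is present. The document gives no effect size, SD or power, so there is no planned figure to reproduce. The false-positive rates need none of these.

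**1. Between groups: no true effect, one time point, 400,000 simulated trials per setting**

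| Reading | 24 per arm | 20 per arm |
|---|---|---|
| t-test, one contrast | 5.0% | 5.0% |
| t-test, two contrasts against Control | 9.1% | 9.1% |
| t-test, all three pairs, unadjusted | 12.2% | 12.2% |
| ANOVA F | 5.0% | 5.0% |
| ANOVA, pairs only after a significant F | 5.0% | 5.0% |
| ANOVA, Tukey | 5.0% | 5.0% |
| ANOVA, pairs neither gated nor adjusted | 12.2% | 12.1% |

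Analytic check of the last row: P(Q > √2 × t at 0.975), with Q the studentized range for 3 groups and 69 df, is 12.1%. The independence formula, 1 − 0.95³ = 14.3%, overstates the rate because the pairs share groups. Unequal splits of the 72 (18/27/27 and 36/18/18) leave the three-pair t-test rate at 12.0% to 12.1%.

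Each sentence spans about 5% to 12%. The position within that range depends on gating, adjustment or a single contrast.

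**2. How often the two routes disagree, 24 per arm**

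| Pairs t-tested | True means (SD units) | t significant, F not | F significant, t not |
|---|---|---|---|
| All three | no effect | 7.2% | 0 |
| All three | 0/0.4/0.8 | 13.1% | at most 1 in 100,000 |
| Two, against Control | no effect | 5.0% | 0.8% |
| Two, against Control | 0/0/0.8 | 5.0% | 6.5% |
| One contrast | no effect | 2.5% | 2.4% |
| One, rTMS vs rTMS+BT | 0/0.4/0.8 | 1.4% | 42% |

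The first row agrees with step 1: 12.24% − 5.03% = 7.21%. The non-zero means are assumed.

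**3. The open time point**

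Suppose a positive result at any of the three post-treatment times could be claimed, with an assumed correlation between times of 0.5 to 0.9. The chance of at least one false positive is then about 9% to 13% with the F-test alone, and about 20% to 28% with all three pairs t-tested unadjusted. This is a separate contribution that the single-time-point figures in step 1 do not contain.

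**4. Before and after within one group, read literally**

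With SD σ and correlation ρ, the mean change has true variance 2σ²(1 − ρ)/n. One-way ANOVA uses 2σ²/n, too large by a factor 1/(1 − ρ): 2 at ρ = 0.5 and 10 at ρ = 0.9. Simulation with 100,000 replicates, for assumed ρ from 0.5 to 0.9:

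| Quantity | One-way ANOVA | Paired test |
|---|---|---|
| False-positive rate, n = 24 | 0.7% falling to 0.0% | about 5% |
| Power for an assumed 0.5 SD gain, n = 24 | 36% falling to 27% | 65% rising to over 99% |
| Power for an assumed 0.5 SD gain, n = 20 | 29% falling to 17% | 57% rising to over 99% |

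**The case against.** The strongest reply is that the two between-group sentences fit together: ANOVA first, with t-tests as the pairwise step. That may well be what was meant, but the text does not say so. A further reply is that the choice of post-hoc procedure, gating and adjustment usually belongs in the SAP, which is not shown. This stands as far as it goes: the absence of those details is not itself the fault. The fault is that the protocol assigns two unranked tests to one comparison and leaves the primary endpoint without a time point.

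A reader might infer that the t-test sentence means 12% and the ANOVA sentence 5%. The document does not support this. It sets the worst reading of one sentence against the best of the other, when both cover the same range. Nor is the t-test always the more lenient route: that holds only if all three pairs are t-tested, which the protocol does not say. With one or two contrasts, disagreement can run either way.

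On the within-group rule, 'one-way ANOVA' may be loose naming for a repeated-measures analysis with time as its only factor. If so, one clarifying word settles it. Even on the literal reading the rule is conservative and concerns change within a group only. The power figures rest on an assumed gain and assumed correlations.

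**Conclusion.** The point holds in three parts.

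- **Between groups.** Which test decides the primary FMA result is not fixed. At one time point, with 24 per arm assumed and two-sided 0.05, the false-positive chance is about 5% to 12% under either sentence. At 20 per arm each rate is within 0.2 percentage points. The two routes can give opposite primary verdicts. The direction is fixed (t-test significant, ANOVA not, in about 7% of trials with no effect) only if all three pairs are t-tested.
- **Time point.** Three post-treatment FMA assessments compete to be primary.
- **Within groups.** Read literally, the rule has a true size below 1% and loses much of the power of a paired test. It does not add to between-group false positives, so it should not be counted as a further inflation of the 12%.

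The first two parts can decide the primary result and must be settled before outcome data are seen. The third is a needed correction of lesser consequence.

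**What to change.** - Name one primary FMA time point in advance and treat the others as secondary. The sponsor chooses which.
- Make one between-group analysis primary. It can be the three-group ANOVA, with pairwise tests (including any t-tests) done only after a significant F or with Tukey adjustment. Alternatively, it can be one contrast named in advance. Deleting the t-test sentence alone is not enough, because post-hoc tests that are neither gated nor adjusted stay at about 12%.
- For change within a group, replace one-way ANOVA with a paired or repeated-measures test, or state that repeated-measures ANOVA is meant.

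The cost is protocol wording, fewer results that can be called confirmatory and, with Tukey, lower pairwise power. For an assumed 0.8 SD difference the noncentrality is 0.8 × √(24/2) = 2.77 at 24 per arm. Power is 77% with the unadjusted t-test (46 df) and 65% with Tukey (critical value 2.395, 69 df). At 20 per arm it falls from 69% to 55%. A single contrast named in advance avoids this loss.
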